The study population encompasses patients that are attributed to primary care clinics in one of the four health systems defined above. Patients are included in the study if they are ages 19 or older and received two or more outpatient visits at a participating practice during a one-year period before the COVID-19 pandemic, and had one or more of five chronic illnesses (asthma, chronic obstructive pulmonary disease (COPD), congestive heart failure (CHF), diabetes, hypertension) as defined by the Medicare Chronic Conditions Warehouse algorithm.²⁷ For the claims analyses, we additionally require that patients are continuously enrolled over the entire study time period.

Interventions and Comparators

We will use natural variation in the availability of in-person and telemedicine visits across clinics over time during the pandemic in a difference-in-differences framework to compare the clinical effectiveness of three care models: (1) telemedicine-only; (2) telemedicine-supplemented in-person visits; and (3) in-person visits only.

While these arms will be defined at onset of the pandemic, clinics may not remain in the same arm over time. We will evaluate changes in total telemedicine and in-person visits in each month and capture the status of each clinic by month for secondary analyses. In additional secondary analyses, we will explore heterogeneity in effects across patient and organizational subgroups.

The intervention population encompasses patients that are attributed to primary care clinics that switched to delivering telemedicine-only visits as their primary model of care delivery during the pandemic. We will compare this population to patients that are attributed to clinics that delivered telemedicine-supplemented in-person visits or in-person visits only during the pandemic. We will define the clinics' primary model of care delivery, and the timing of their switch in clinical modality, using the survey results from Aim 1.

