Our decision to make the clinic the primary unit of analysis is because of the known sociodemographic and clinical differences in patients (pre-pandemic) who chose to use telemedicine. Patients that use telemedicine for instance, tend to be younger and are more likely to be female than patients that used other sites of care.²⁸ Therefore, in our primary analysis, we will exploit the change in availability for telemedicine services at the clinic level as an independent determinant of telemedicine use, leveraging an intent-to-treat approach to evaluate the association between clinic-level telemedicine availability and patient outcomes. We will further improve the internal validity of the study by matching clinics using clinic-level characteristics. This is further described in the analytic methods below.

Outcomes

We will analyze measures of health care utilization and quality from Medicare and commercial (Anthem and Humana) claims and CRN EHR data. Our primary outcome measures include avoidable emergency department (ED) admissions, potentially preventable hospital admissions, and continuity of care.²³ Secondary measures will include evidence of

PRINCIPAL INVESTIGATOR: [name]; [name]

controlled disease (as indicated by condition-specific measures endorsed by the National Quality Forum (NQF) or HEDIS) and days at home. A list of outcome measures is included in Table 1 below. These primary and secondary outcome measures will be constructed at the patient-month level, and we will examine 30-day, 60-day, 6-month and one-year outcomes where data are available. We have operationalized the majority of these measures through a previous PCORI health system demonstration grant, in collaboration with OneFlorida.

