Our primary analysis will be the Medicare claims data analysis. We anticipate this will be the most robust analysis because of the large sample size (relative to the commercial claims data) and ability to comprehensively track patients across care settings (relative to the CRN EHR data). We will obtain 100% of 2017 through Q1 2021 Medicare fee-for-service claims data for the three states in which CRN-participating research sites are located (FL, NC, and NY). Therefore, we will be able to follow patients regardless of where they seek care, which will improve patient attribution, as well as capture the entirety of a patient's follow-up care for the utilization, continuity of care, and quality of care measures. The Medicare data will be accessed via the Centers for Medicare and Medicaid Services Virtual Research Data Center (VRDC), because (in contrast to physical copies of the data), the VRDC allows for data to be used for analysis with little lag (approximately three months following claims run-out). Use of the VRDC will enable the research team to include up to 11 months of data following the initial apex of the pandemic in April 2020. The patient attribution process will be separately conducted for each enrollee population.

Unfortunately, it will not be feasible to use federal (T-MSIS) Medicaid claims data for this project. The T-MSIS data are currently running at a 2-year lag, meaning we would not be able to obtain the data for much of the period of interest until after the grant had concluded.

In the secondary analysis, we will replicate the Medicare analysis using commercial claims data for commercially insured populations. Commercial claims data will be analyzed for Anthem and Humana commercial enrollees at the NY, FL, and NC sites for 2017 through Q1 2021, using the same analytic approach.

An additional secondary analysis will examine measures of disease control (see Table 1), utilization, and continuity of care drawn from the CRN data. Measures of disease control require EHR data that in general are not available from the commercial claims providers. In addition, the CRN data are all-payer. However, the main limitation is that if patients seek care outside of the CRN, we will not capture their utilization within CRN data. Therefore it would not be appropriate to seek to extract the ED or hospital admission data from this source.

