We propose a causal model informed by the Wagner Chronic Care Model in which productive disease management interactions between informed patients and prepared care teams are promoted by effective health systems as well as communities.³⁷ Critical relevant elements of the health system are processes to provide self-management support, design of the healthcare delivery system, and technologies such as clinical information systems and decision-support. In our causal model, for patients with chronic disease, access to care is a mediator in the causal pathway between the disruption in care from the pandemic and the outcomes in our study (e.g., unnecessary utilization such as unplanned ED visits, and satisfaction with care). To the extent that telemedicine improves access to care, it mediates this relationship. Furthermore, patient-provider communication is an additional mediator of this relationship, through its effect on self-management support as well as trust in the healthcare system.

However, one reason this study is important is that the abrupt nationwide transition makes it challenging to determine in advance whether telemedicine would be expected to have positive or negative impacts on care access and patient-provider communication, overall and within important patient subgroups. The pandemic prompted telemedicine use by patients who would otherwise not have been early adopters of telemedicine, increasing the diversity of patient users, including those from disadvantaged social circumstances or with older age who may encounter more barriers to successful use of telemedicine (stemming from limited device access, technology literacy, or broadband access, or primary language). These barriers would cause telemedicine to have a negative effect on care access and patient-provider communication, as well as patient satisfaction. Conversely, however, there are known instances in which people who would not have opted into the technology themselves nevertheless become effective users of the technology after being provided with an initial access experience.²⁶ Thus, the forced use of telemedicine may possibly have successfully promoted engagement with telemedicine and therefore improved access to care and patient-providers communication among some patients from less advantaged patient groups.

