In order to further improve the comparability of clinics across each of the treatment arms, we will use propensity scores to match clinics based on clinic-level characteristics, including rurality; size; mean clinical risk (HCC score, Elixhauser comorbidity index); and proportions of patients with Medicaid coverage, dually eligible for Medicaid and Medicare, 65 and older, male, and black or Hispanic. In an additional sensitivity analysis, we will exclude patients who tested COVID-positive. We will match clinics based on their baseline characteristics in the pre-pandemic period and their initial treatment arm status after the onset of the pandemic. In addition, we will explore the sensitivity of our estimates to re-matching each month, since, as noted in the intervention section above, treatment status will be time-varying. As part of our descriptive analysis, we will evaluate how often clinics switch treatment arms from their initial treatment status, which will inform our sensitivity analyses.

We recognize that it is possible that the matching procedure might result in the loss of clinics and sample size. If it does, we would instead apply alternative methods that accomplish the goal of propensity score matching (addressing confounding to improve causal estimation) without loss of sample size. The first alternative is inverse probability weighting, which uses the propensity score to re-weight the outcomes, creating a pseudo-sample in which exposure to the intervention is unrelated to potential confounders.⁴¹ The second alternative is doubly robust estimation, which incorporates (i) a propensity score model and (ii) an outcome regression model in order to gain efficiency (more power) in comparison to an inverse weighting, and to reduce reliance on the ability of correctly positing the propensity score model.⁴² We can substitute these approaches for the originally proposed propensity score weighting, or we can instead apply them in a sensitivity analysis.

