The goal of these subgroup analyses is to evaluate the effects of each of the three telemedicine arms across patient populations which may have unequal access to telemedicine visits, experience differential treatment effects of telemedicine use, and vary in experiences with regards to using telemedicine. In particular, individuals with lower digital health literacy and higher illness burden may be affected differentially by the adoption of telemedicine-supplemented or telemedicine-only care relative to in-person care only. Previous work has also shown that older adults (aged 65 and older) have lower digital health literacy, and individuals in rural areas are more likely to face greater barriers accessing telemedicine.^{44,45} Previous work has also reported that black patients were less likely to use an inpatient portal relative to white patients, although recent work has shown that during the COVID-19 pandemic, blacks may be more likely than whites to report using telemedicine.^{46,47} We hypothesize that the comparative effectiveness of the treatment arms will differ significantly across the following subgroups: race/ethnicity, rurality, income as proxied by payer and median income for zip code.

G. ETHICS AND DISSEMINATION – AIMS 1 AND 2

Research Ethics Approval

PRINCIPAL INVESTIGATOR: [name]; [name]

BRANY, an independent fully AAHRPP-accredited IRB, will serve as the IRB of record for this study. An exempt approval was received by BRANY on 11/16/2020. Local IRBs will be obtained at the participating sites by the expected deliverable date (2/15/21).

All protocol modifications will be disseminated to relevant parties, including all participating investigators and sites, the IRB, and PCORI.

Confidentiality

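### In the primary Medicare analysis the only age term listed for clinic matching is the share aged 65 and older, and age is not a subgroup although the plan names older age as a barrier to telemedicine

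*Combined protocol and SAP*

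**What the plan says.** **Population.** Section F, Data Collection Methods and Data Sources: "Our primary analysis will be the Medicare claims data analysis". The same section adds: "The patient attribution process will be separately conducted for each enrollee population". Section E, Eligibility Criteria, sets the lower age limit: "Patients are included in the study if they are ages 19 or older". Medicare patients under 65 are therefore eligible.

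**Matching.** Section F, Statistical Methods, Primary Analysis, lists rurality, size, mean clinical risk and a set of patient shares for the clinic propensity score. Age enters only as one of those shares: "proportions of patients with Medicaid coverage, dually eligible for Medicaid and Medicare, 65 and older, male, and black or Hispanic". The plan does not say whether these shares are computed on a clinic's Medicare patients or on its whole panel.

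**Adjustment.** Adjustment for patient-level characteristics is stated only for the secondary as-treated analysis. The doubly robust alternative includes an outcome regression but names no covariates for it. Balance before and after matching will be reported, without a list of covariates.

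**Age as a reason for different use or effect.** Three places mention it:
- Interventions and Comparators says that patients who chose telemedicine before the pandemic "tend to be younger and are more likely to be female than patients that used other sites of care".
- The causal model describes new users of telemedicine, "including those from disadvantaged social circumstances or with older age who may encounter more barriers to successful use of telemedicine".
- Heterogenous Treatment Effects says that "older adults (aged 65 and older) have lower digital health literacy".

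**Subgroups.** Heterogenous Treatment Effects announces eight subgroup analyses and then states hypotheses for race/ethnicity, rurality and income. Age is in neither list.

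**The concern.** Two clinics can have the same share of patients aged 65 and older while one serves mainly people in their late sixties and the other mainly people over 80. The listed matching term treats them as equal on age. In a Medicare cohort this is where most of the age range is likely to lie.

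The difference-in-differences removes any age effect that is constant over time. It does not remove a change that starts with the pandemic and differs by age, such as older patients cutting back ED visits more sharply than younger ones. If the arms differ in age above 65 after matching, that differential change is credited to the care model. The planned check of trends covers only the months before onset, so it says nothing about a divergence that begins at onset.

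The subgroup gap is separate and needs no assumption. The plan gives reasons why older patients might benefit less and then has no Aim 2 analysis that looks. Older and younger patients are contrasted only as a possible comparison in the Aim 1B interviews.

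**Working it through.** **1. Is age one of the eight subgroup analyses?** The list in Heterogenous Treatment Effects gives:
- sociodemographic: race/ethnicity, rurality, zip-code income (3);
- clinical: COVID-19 status, illness burden, stable versus unstable disease (3);
- telemedicine factors from the Aim 1 survey, counted as one (1);
- dual eligibility (1).

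3 + 3 + 1 + 1 = 8, which reproduces the plan's count (9 if the two named telemedicine factors are counted separately). Age is not among them on either count.

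**2. What equal 65+ shares leave unbalanced.** The documents give no age distribution, so these inputs are assumed: mean age 53 (SD 9) below 65 and 75 (SD 7) at 65 and over, a difference of 22 years. Take two clinics with the same 65+ share p whose mean ages among patients 65+ differ by 4 years. The overall gap is p × 4.
- p = 0.85: gap 3.4 years. Total SD = √(0.85×0.15×22² + 0.85×49 + 0.15×81) = 10.75. Standardized difference 3.4/10.75 = 0.32.
- p = 0.95: gap 3.8 years. Total SD 8.58 by the same formula. Standardized difference 0.44.

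**3. How informative is the 65+ share?** At the patient level, the fraction of age variance captured is p(1−p)·22² / [p(1−p)·22² + p·49 + (1−p)·81]. For p = 0.80, 0.85, 0.90, 0.95 and 0.99 this gives 58%, 53%, 45%, 31% and 9%.

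At the clinic level, the fraction of variance in clinic mean age captured is (22·s)² / [(22·s)² + (p·m)²]. Here s is the SD of the share across clinics and m is the SD across clinics of mean age among patients 65+. With p = 0.90 and m from 3 years down to 1:
- s = 2 points: 3% to 19%;
- s = 5 points: 14% to 60%;
- s = 10 points: 40% to 86%.

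The term runs from nearly useless to fairly informative, depending on spreads that the documents do not give.

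**4. Size of a possible bias in ED use.** Assume both arms are 85% aged 65+, so the listed term shows no difference. Let the share aged 75+ differ by d = 5 to 15 points. Let ED use fall by 15% at 65–74 and by 20% to 30% at 75+. The spurious difference between arms is d × (fall₇₅·rate₇₅ − fall₆₅·rate₆₅).

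| Assumed ED rates | Smallest | Largest |
|---|---|---|
| 18% at 65–74, 24% at 75+ | 0.05×(0.20×0.24 − 0.15×0.18) = 0.11 points | 0.15×(0.30×0.24 − 0.15×0.18) = 0.68 points |
| 20% in both | 0.05×(0.20×0.20 − 0.15×0.20) = 0.05 points | 0.15×(0.30×0.20 − 0.15×0.20) = 0.45 points |
| 5% in both | 0.05×(0.20×0.05 − 0.15×0.05) = 0.01 points | 0.15×(0.30×0.05 − 0.15×0.05) = 0.11 points |

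Under these inputs the arm with more patients aged 75+ would seem to have the larger fall. The 5% and 20% rates are the ends of the range in the Power Calculation. Every other input is assumed, and d is the gap before any reduction from matching on the other characteristics. The 1-point ED margin in that section is a yardstick only, because it applies if a non-inferiority framework is adopted.

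**5. Duplicate term.** If the shares are computed in a Medicare cohort, a patient with Medicaid coverage is by definition dually eligible, so two of the listed variables become one.

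**The case against.** The strongest defence is that age is already handled in several ways. The 65+ share is matched. The list opens with the word including, so finer age terms are not ruled out. Mean HCC and Elixhauser scores are matched and may carry part of the age signal. Balance will be reported. The design removes stable differences, so bias needs residual age imbalance, age-specific pandemic trends, and alignment of the two with arm. On subgroups, the plan contrasts people 65 and over with younger adults and does not claim that effects differ between, say, 65–74 and 85+. The commercial claims replication also offers an indirect look at another population.

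Much of this stands, and it rules out four stronger readings that a reader might infer:
- *The 65+ share hardly varies in Medicare.* No document figure supports this, and step 3 shows a wide range. The shares may not even be Medicare-only: separate attribution by enrollee population suggests that they are, while listing Medicaid coverage apart from dual eligibility suggests an all-payer panel.
- *All-payer shares would mostly describe patients outside the analysis.* That needs a payer mix the documents do not give.
- *Age is left unbalanced.* It is coarsely balanced, with no listed term for age above 65.
- *The plan itself calls age a confounder.* Its remark about younger users concerns patients' own choice of telemedicine and is the reason for defining exposure by clinic. It does not say that clinics with older panels adopted differently, and the plan expects the switch to be potentially unrelated to patient outcomes.

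What the defence does not answer is that an open list and an unspecified balance table commit nobody to a finer age measure. Comorbidity means do not guarantee age balance, and the pre-period test cannot see a divergence at onset. The commercial comparison mixes payer with age. Bands within 65+ go further than the plan's own rationale, but with an under-65 band they also cover the contrast it does state.

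**Conclusion.** The point holds as a moderate one that should be fixed. Four things follow from the text alone: the 65+ share is the only listed age term, it cannot balance age within the 65+ group, patient-level adjustment is not stated for the primary model, and age is absent from both the subgroup list and the stated hypotheses.

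Whether this biases the primary result is unknown. The range of about 0.01 to 0.7 points rests on assumed age gaps, assumed falls in ED use and, in its upper part, assumed ED rates, with no credit for the other matching variables. At the lower end it is negligible. At the upper end it would be a material part of a 1-point difference. The missing test of effect modification by age depends on none of these assumptions.

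**What to change.** **Primary Analysis, matching.** For the Medicare analysis, state that the matching shares are computed in each clinic's attributed Medicare cohort. Add mean age, or age-band shares with one band omitted as reference (for example under 65, 75–84 and 85+, with 65–74 as reference), to the propensity score and the balance table. If bands are used, the under-65 share replaces the 65+ share, because one is the complement of the other. All four bands sum to 100% and must not be entered together. Drop Medicaid coverage where it duplicates dual eligibility.

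**Primary Analysis, sensitivity.** Add age-band by post-onset-period terms to the event-study model. A full set of age-band by calendar-month terms is not needed: January 2017 to March 2021 is 51 months, so four bands would add about (4 − 1) × (51 − 1) = 150 parameters.

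**Heterogenous Treatment Effects.** Add age band as a ninth pre-specified subgroup with an interaction test, and keep the COVID-19 subgroup.

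**Cost.** The data-source table already lists demographic characteristics for the Medicare claims, so no new collection should be needed. The extra propensity terms may cost some clinic matches, for which the plan already provides weighting and doubly robust alternatives. There is also one more subgroup comparison to interpret.

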• Avoidable ED Admissions³⁰	Claims
• Potentially Preventable Hospital Admissions^{*31,32}	Claims
• Continuity of Care	
○ Bice-Boxerman Continuity of Care Index	Claims
○ Breslau Usual Provider of Care	Claims
○ Attendance at Follow-up Appointment	EHR

PRINCIPAL INVESTIGATOR: [name]; [name]

• Patient-Reported Outcomes	REDCap
SECONDARY OUTCOMES	
• Days at Home (days per month not in hospital or institutional setting)	Claims
• Evidence of controlled disease**	EHR/Claims

*Potentially preventable hospital admissions are defined as hospital admissions for ambulatory care-sensitive conditions, which can be treated with primary care

**In subset analyses for which we have a consistent panel of EHR data, we will assess condition-specific measures of disease control, including measures accredited by the NQF or included in HEDIS. These may include laboratory measurements, vitals, or medication use. The choice of these measures will be informed by provider and patient participants in our Accelerator (Stakeholder Board) in order to ensure we select outcomes that are important to stakeholders.

Participant Timeline

The main outcomes of interest will be assessed 30-days, 60-days, 6 months, and 1 year after the exposure to one of the comparator arms of clinic-level telemedicine use. Our study will include claims data for 2017-Q1 2021 and CRN EHR data for 2017-Q1 2021.

Sample Size

The estimated breakdown of the number of primary care patients in each of the four participating health systems by race and ethnicity is shown in Table 2.

Table 2

Part A. Baseline estimates of demographics of primary care patients from 4 health systems				
Ethnic Category	Females	Males	Sex/Gender Unknown or Not reported	Total
Hispanic	6772	3475	0	10247
Not Hispanic	89657	59527	2	149186
Unknown (individuals not reporting ethnicity)	26863	19569	2	46434
Ethnic Category: Total of All Subjects	123292	82571	4	205867
Racial Categories				
American Indian	120	78	0	198
Asian	5733	3736	0	9469
Native Hawaiian or Other Pacific Islander	184	93	0	277
Black or African American	22084	11060	0	33144
White	60479	44323	0	104802
More than one race	6236	3248	0	9484
Unknown or not reported	28456	20033	4	48493
Racial Categories: Total of All Subjects	123292	82571	4	205867
Part B. Primary care patients from 4 health systems with Hispanic/Latino ethnicity				
Racial Categories	Females	Males	Sex/Gender Unknown	Total

PRINCIPAL INVESTIGATOR: [name]; [name]

			or Not reported	

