Data Organization: All final analytic files for CRN and claims data analyses will be organized as patient-month records and generated and stored as comma-separated values files. We will collect PROs through survey data using RedCAP, a HIPAA-compliant IRB-approved platform. For the PRO analysis, analytic files will be organized as patient-encounter records and stored as comma-separated values files.

Data Handling: Medicare claims data will be accessed within the VRDC, and will be accessed and managed according to the Medicare specifications described in the DUA. Only 4 analysts will have access to VRDC. The VRDC will handle data backups. Commercial claims data will be handled within the commercial entity, with specified users described in the DUA.

CRN data and PRO data will both be handled within the Weill Cornell Data Core, a highly secure data repository and analytic environment maintained by Weill Cornell Information Technology Services. This restricted-access data center that meets the security requirements for PHI and other data designated as restricted access. Data Core's computing system belongs to a Windows domain that exceeds the U.S. Defense Department's C2 standards for trusted computing environments. Access is limited to authorized users who have signed a DUA with the Data Provider and a Computing System User Agreement with HPR Data Core, as confirmed by the WCM Office of Sponsored Research Administration and IRB. Data is backed up daily.

For all data sources, privacy and confidentiality will be maintained in accordance with IRB requirements. To limit risk, analyses will be performed on limited data sets, including no individually identifying information other than dates.

PRINCIPAL INVESTIGATOR: [name]; [name]

Data Description: We will utilize existing PCORnet CDM and Medicare LDS data dictionaries. A separate data dictionary will be developed for the PRO data. For in-house data sets, metadata will be documented within the Weill Cornell Data Catalog, which utilizes the elements from Dublin Core, with additional elements added from the following standards:

- Common metadata elements for Cataloging Biomedical Datasets
- DataCite Metadata
- Dryad Metadata
- W3C Data Catalog Vocabulary
- NIH BioCADDIE Metadata v1

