We will define the degree of telemedicine exposure (dose) in two ways. First, based on the comprehensive landscape survey of primary care leaders in [Aim 1](#), we will develop a composite score indicating the robustness of the telemedicine program at each clinic site under study. Among other features, this score will take into account the total number of components and delivery modes of the telemedicine program, its focus on providing coordinated care to a patient population with chronic care needs, and staff and clinical support from the organization.

Second, we will define telemedicine exposure based on the proportion of all visits at a given clinic that are delivered via telemedicine in each month. Specifically, we will classify clinics into quartiles of telemedicine exposure based on the distribution of all telemedicine provision among clinics in this treatment arm. We will then separately analyze the relationship between our outcomes of interest and the amount (dose) of telemedicine being offered at a clinic. We will cluster all primary and secondary analysis at the clinic level, as this is the level at which the exposure occurred.⁴³

Finally, in addition to the primary intent-to-treat analysis, we are proposing an additional secondary analysis. This secondary “as treated” analysis is designed to evaluate the relationship between patient-level telemedicine exposure and our outcomes of interest. In this secondary analysis, we will characterize patients’ exposure to telemedicine after the first wave of shelter-in-place measures were put into place based on the treatment that they actually received

PRINCIPAL INVESTIGATOR: [name]; [name]

rather than based on the availability of telemedicine at the primary care clinic to which they were attributed. In this analysis, we will adjust for observed clinic and patient-level characteristics as described in the response above that may impact both the availability and choice to use telemedicine, as well as patient outcomes. Additionally, we will provide estimates from a fixed effects model in which each patient serves as their own control.

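### The secondary as-treated analysis does not require patient-level telemedicine exposure to precede the outcome, so visits triggered by an ED visit or admission can count as exposure

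*Combined protocol and SAP*

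**What the plan says.** Section F, Statistical Methods, Primary Analysis adds a secondary as-treated analysis "designed to evaluate the relationship between patient-level telemedicine exposure and our outcomes of interest". It characterises each patient's "exposure to telemedicine after the first wave of shelter-in-place measures were put into place based on the treatment that they actually received". The text sets no end to this exposure period, no patient-level index date and no patient-level categories.

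The outcome clock is set elsewhere. Under Participant Timeline in Section E, the main outcomes "will be assessed 30-days, 60-days, 6 months, and 1 year after the exposure to one of the comparator arms of clinic-level telemedicine use". That clock starts with the clinic, not with the patient's own first telemedicine visit.

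Two safeguards are named for the as-treated analysis: "we will adjust for observed clinic and patient-level characteristics as described in the response above", and "estimates from a fixed effects model in which each patient serves as their own control".

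The data structure would support a time-ordered analysis. Section E, Outcomes says that "primary and secondary outcome measures will be constructed at the patient-month level", and Section F, Data Organization says "All final analytic files for CRN and claims data analyses will be organized as patient-month records". The Medicare data source is expected to "include up to 11 months of data following the initial apex of the pandemic in April 2020".

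**The concern.** Exposure and outcome can accrue over the same months, and nothing puts exposure first. A patient who goes to the ED in month 4 may have a telemedicine follow-up the same month. Under the rule as written that visit can classify the patient as exposed, and the ED visit is then attributed to telemedicine.

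The named safeguards address other problems. Adjusting for observed characteristics deals with which patients choose telemedicine. Patient fixed effects remove stable differences between patients. Neither deals with an outcome that causes the exposure within a patient. The time-varying status described in Sections E and F belongs to clinics and carries no lag.

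At stake is the credibility of the planned analysis that speaks most directly to patients' own use of telemedicine. With samples this large, such a bias would be estimated precisely and could be taken for a real effect.

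**Working it through.** **Inputs from the documents.** ED risk of 5% to 20% in the in-person arm, 25,000 patients per group, a 1-point margin and one-sided 2.5% (Section E, Power Calculation); up to 11 months of data after April 2020 (Section F, Data Collection Methods and Data Sources). The plan gives no period for the 5-20% risk; here it is taken as the risk over follow-up.

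**The plan's own figure.** There is none for the as-treated analysis. The non-inferiority power that uses these ED rates is Φ(0.01/√(2p(1−p)/25,000) − 1.96).
- p = 0.20: Φ(2.795 − 1.96) = 79.8%, against a stated 80%.
- p = 0.05: Φ(5.130 − 1.96) = 99.9%, against a stated 99%.

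The figure reproduces.

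**Closed-form check under no effect, any versus no telemedicine.** Let p be the monthly chance of an unrelated telemedicine visit (5% or 10%), f the share of ED patients who get telemedicine follow-up (5% to 40%), and R the ED risk (5%, 10%, 20%). The values of p and f are assumptions. Over 12 months:
- P(exposed | no ED) = 1 − (1−p)^12
- P(exposed | ED) = 1 − (1−p)^12 × (1−f)
- ED risk by exposure follows from Bayes' rule.

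*Upper end* (p = 0.05, f = 0.4, R = 0.05): 0.95^12 = 0.5404, so the exposure probabilities are 0.4596 and 0.6758. P(exposed) = 0.05×0.6758 + 0.95×0.4596 = 0.4704. ED risk is 0.0338/0.4704 = 7.2% in the exposed and 0.0162/0.5296 = 3.1% in the unexposed. The ratio is 2.35.

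*Lower end for f = 0.2* (p = 0.10, R = 0.20): 0.90^12 = 0.2824, so the exposure probabilities are 0.7176 and 0.7741. P(exposed) = 0.2×0.7741 + 0.8×0.7176 = 0.7289. ED risk is 0.1548/0.7289 = 21.2% against 0.0452/0.2711 = 16.7%. The ratio is 1.27.

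| Telemedicine follow-up after ED (assumed) | False risk ratio over the grid |
|---|---|
| 5% | 1.06 to 1.11 |
| 10% | 1.12 to 1.23 |
| 20% to 40% | 1.27 to 2.35 |

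With 11 months in place of 12, the last row is about 1.29 to 2.43.

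**Simulation under no effect, by contrast.** 200,000 patients, 11 months, ED risk 5% or 20%, no confounding. Assumed: telemedicine visits in 2%, 5% or 15% of patient-months, in-person visits in 10%, and 10% to 40% of ED visits followed in the same month by a visit of each type.
- *Any versus none:* +0.6 to +9.1 points at 5% ED risk and +2.0 to +27.9 at 20%. One case: 24.4% against 16.4% (+8.0) at 20% ED risk, 5% background telemedicine and 20% follow-up by each mode.
- *Supplemented versus in-person-only:* +0.8 to +28.7 points.
- *Telemedicine-only versus in-person-only:* +24.6 points (37.7% against 13.1%) when 40% of ED visits lead to telemedicine and 10% to in-person, with 2% background telemedicine; −8.4 points (12.8% against 21.2%) when the two follow-up shares are reversed, with 15% background. Post-ED in-person visits move patients out of the telemedicine-only group.
- *Patient fixed effects, same-month exposure:* +0.3 to +8.5 points per month at 5% ED risk and +1.3 to +28.7 at 20%.
- *No ED-triggered visits:* no bias beyond simulation noise.

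**Checking the repair.** A landmark (exposure in months 1-3, ED visits from month 4) gave differences within about ±0.6 points, which is noise. A one-month lag without patient effects gave about ±0.15. With patient fixed effects, a lag alone gave false protection of about 0.1 to 1.4 points per month, on monthly ED rates of about 0.5% and 2.0% (11 months, p = 5-10%, f = 20-40%). Coding exposure as ever exposed up to the previous month gave 0.3 to 4.2. The reason is that past outcomes still drive exposure, which violates strict exogeneity in a short panel. A matching prior-ED term largely removed it.

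**The case against.** The plan leaves a gap; it does not state a faulty rule. A reader might infer that it deliberately counts post-ED visits as exposure over the whole follow-up. It does not say so: the window is unspecified, and the Section E paragraph on patient-reported outcomes leaves the duration of patient exposure to stakeholder input and the Aim 1A survey. That stands. But the wording sets no order, and analysts could follow it to the letter and produce the bias.

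A reader might also infer that a null effect must look harmful. That holds for two contrasts and fails for telemedicine-only against in-person-only, where the sign depends on how ED patients are followed up. Nor can one say that patients with few visits are unexposed by definition, since no patient-level categories are defined.

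The size rests on assumed visit and follow-up rates. That stands, and low follow-up gives a modest bias. Calling the bias larger than any plausible effect is not supported: the plan itself cites ED reductions of 9% to 54% from other interventions, and a ratio of 1.27 is of that order.

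Finally, this is a secondary analysis, and it may not be the only one below clinic level: a note in Section F says new network data may allow a visit-level comparison. Both points limit the consequence and leave the ordering gap in place.

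**Conclusion.** The concern holds for the secondary as-treated analysis. As written, that analysis lets a visit caused by an ED visit or admission count as exposure, and neither named safeguard corrects this. Under no true effect the bias is toward harm for any versus no telemedicine and for supplemented versus in-person-only care. It can go either way for telemedicine-only versus in-person-only care.

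Its size cannot be fixed from the documents. Only the 5-20% ED risk comes from the plan. In the one-year ever/never model, the false risk ratio runs from about 1.06 with 5% telemedicine follow-up after an ED visit to 2.35 with 40%. For scale, the plan's non-inferiority margin is 1 percentage point, and most of the simulated differences exceed it.

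The primary intent-to-treat analysis classifies by clinic-level availability and is not affected. The documents do not support a claim that the main result is at risk, or that the as-treated result is bound to contradict it. The change should be made before the as-treated analysis is run.

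**What to change.** Define the patient-level exposure categories and the period in which they are determined. Then use one of these:

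- **(a) Landmark.** Classify exposure in a fixed early window and count outcomes only afterwards.
- **(b) Lagged exposure.** On the patient-month file, let exposure through month t−1 predict outcomes in month t, adjusting for ED visits and admissions before t. The adjustment is needed because, unlike in the simulation, real ED visits cluster within patients.

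In the patient fixed-effects model, include the prior ED/admission term as well as the lag, coded in the same form as exposure (previous month with previous month, ever with ever). The lag alone leaves a false protective bias that is small in absolute points but not small against the monthly ED rate.

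Cost: SAP wording and some programming on files already planned. The landmark loses all outcomes in its window (3 of up to 11 months in the example above), including the early 30- and 60-day outcomes. The one-month lag loses the first month.
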